### 2. ABBREVIATIONS

%CV Percent coefficient of variation

ACEI Angiotensin converting enzyme inhibitor

AE Adverse event

ALT Alanine aminotransferase
AST Aspartate aminotransferase

AUC Area under the plasma concentration-time curve

BD Bronchodilator

BID Twice daily (bis in die)

BMI Body mass index

CGIC Clinician Global Impression of Change CKD-EPI Chronic Kidney Disease Epidemiology

Cmax Maximum plasma concentration

CQLQ Cough-Specific Quality of Life Questionnaire

CRO Contract Research Organization

CT Computed tomography

CYP Cytochrome P450

DMP Data management plan

ECG Electrocardiogram

eCRF Electronic case report form

eGFR Estimated glomerular filtration rate

FDA Food and Drug Administration

FEV1 Forced expiratory volume in 1 second

FSH Follicle-stimulating hormone

FVC Forced vital capacity
GCP Good Clinical Practice

[figure not shown]
GERD Gastroesophageal reflux disease

HbsAg Hepatitis B surface antigen

HBV Hepatitis B virus
HCV Hepatitis C virus

HDL High-density lipoprotein

CONFIDENTIAL Page 18 of 68

HIV Human immunodeficiency virus

ICF Informed consent form

ICH International Council for Harmonisation of Technical Requirements

for Pharmaceuticals for Human Use

IP Investigational product

IRB Institutional Review Board

ITT Intent-to-Treat

IUD Intrauterine device

LCQ Leicester Cough Questionnaire

LTRA Leukotriene receptor antagonist

MAD Multiple ascending dose

MCH Mean corpuscular hemoglobin

MCHC Mean corpuscular hemoglobin concentration

MCV Mean corpuscular volume

MDA Malondialdehyde

MedDRA Medical Dictionary for Regulatory Activities

NAEB Non-asthmatic eosinophilic bronchitis

NASH Nonalcoholic steatohepatitis

PGIC Patient Global Impression of Change

PK Pharmacokinetic(s)

PP Per protocol

PPI Proton Pump Inhibitor

QTcF QT interval corrected for heart rate using Fridericia's formula

RASP Reactive aldehyde species

RBC Red blood cell

REB Research Ethics Board

RTSM Randomization and Trial Supply Management

SAD Single ascending dose
SAE Serious adverse event
SAP Statistical analysis plan

SARS-CoV-2 Severe acute respiratory syndrome coronavirus 2

sUPCR Spot urine protein to creatinine ratio

CONFIDENTIAL Page 19 of 68

Aldeyra Therapeutics, Inc.

Clinical Trial Protocol: ADX-629-CC-001 Version 2.0, 16 June 2022

SUSAR Suspected unexpected serious adverse reaction

TEAE Treatment-emergent adverse event

UACS Upper airway cough syndrome

VAS Visual analog scale

WHODrug World Health Organization Drug Dictionary

CONFIDENTIAL Page 20 of 68

## 3. BACKGROUND AND TRIAL RATIONALE

# 3.1 Refractory Chronic Cough

Cough represents one of the most frequent complaints leading patients to seek medical attention (Schappert and Burt, 2006), and is a common symptom associated with many other conditions such as respiratory infection, asthma, or chronic obstructive pulmonary disease. In cough guidelines, such as those published by the American College of Chest Physicians and the British Thoracic Society (Irwin et al., 2006; Morice et al., 2006), cough is characterized by the length of time a patient is coughing; acute – up to 3 weeks, sub-acute – from 3 to 8 weeks, and chronic – greater than 8 weeks.

Patients who present to a physician for a persistent cough are evaluated and treated for common causes of cough. Patients who continue to cough are evaluated for conditions that are commonly associated with chronic cough, such as asthma, gastroesophageal reflux disease (GERD), and upper airway cough syndrome (UACS) (Dicpinigaitis, 2011; Morice et al., 2006). A patient may be evaluated for less common diseases based on their history, other symptoms, or physical findings. Patients in whom no treatable cause of their cough can be found are characterized as having "refractory chronic cough" (Gibson et al., 2016).

The prevalence of chronic cough is estimated to affect 11% to 13% of the population (Ford et al., 2006; Song et al., 2014). Patients are most commonly women aged between 45 to 75 years. Chronic cough can seriously impair quality of life as it has physical, social, and psychosocial consequences with a marked effect on quality of life as measured by instruments such as the Leicester Cough Questionnaire (LCQ) (Birring et al., 2003b). The disabling effects of chronic cough are understandable, given that patients with the condition cough hundreds or even thousands of times per day for months to years (Smith et al., 2016).

There is a significant proportion of patients with refractory or unexplained chronic cough who do not respond to treatment of the underlying disease or do not have an underlying condition identified. Treatment options for these patients are very limited (Morice et al., 2006). Patients and clinicians will frequently try over-the-counter agents such as dextromethorphan, guaifenesin, and antihistamines with little benefit. Prescription options in the United States of America (USA) include benzonatate, codeine and related opiate products. Over-the-counter antitussive products that contain antihistamine or dextromethorphan are also widely used for cough, but these compounds have limited efficacy.

## 3.2 ADX-629 Background

Reactive aldehyde species (RASP) such as 4-hydroxynonenal and malondialdehyde (MDA) are toxic mediators of the mammalian immune system and are implicated in numerous disease states. The Sponsor has developed ADX-629, a proprietary new chemical entity for the treatment of chronic diseases with inflammatory and immune-mediated components, including psoriasis, ulcerative colitis, nonalcoholic steatohepatitis (NASH), acute respiratory distress

CONFIDENTIAL Page 21 of 68

syndrome, and other diseases thought to be caused or exacerbated by elevated concentrations of RASP.

ADX-629 is a small molecule formulated for oral administration that binds rapidly and irreversibly to RASP, thus preventing RASP-mediated inflammation and other toxicities.

In addition to nonclinical safety studies, Phase 1 safety testing has been conducted in 85 healthy human volunteers in a single ascending dose (SAD) trial and a multiple ascending dose (MAD) trial. In the SAD trial, 41 subjects received ADX-629 and 13 subjects received placebo across all cohorts. In the MAD trial, 23 subjects received ADX-629 and 8 subjects received placebo across all cohorts. Overall, ADX-629 was found to be safe and well tolerated at the doses explored, including the maximum dose of 600 mg twice daily (BID). The adverse event (AE) profile of ADX-629 was favorable compared to placebo. A total of 6 subjects (9.4%) who received ADX-629 (up to 600 mg BID) had treatment-emergent adverse events (TEAEs) compared to 4 subjects (19.1%) who received placebo. None of the subjects had treatment interrupted or discontinued trial drug in the MAD trial.

CONFIDENTIAL Page 22 of 68

Although PK variability was observed, a linear correlation was evident in maximum plasma concentration ( $C_{max}$ ) and exposure (area under the plasma concentration-time curve [AUC]) with increasing dose. The half-life was consistent across doses and days, with mean values in multiple day exposures ranging between 3.49 and 6.83 hours, supportive of BID administration. Little to no accumulation of the drug was seen across all doses. A  $C_{max}$  of 790 ng/mL (approximately 4  $\mu$ M) and an AUC0-12 of 3400 h\*ng/mL is anticipated given the Day 10 exposure at 300 mg BID (extrapolated from 600 mg BID at steady state). This exposure is expected to yield an adequate molar ratio to achieve stoichiometric efficacy against elevated RASP. A decrease in free MDA levels was observed in the plasma of healthy volunteers over 10 days of dosing with ADX-629 600 mg BID that was statistically significantly greater than that of subjects treated with placebo. Following ingestion of a high-fat meal on Day 10 of dosing with 600 mg BID or placebo, levels of free fatty acids were statistically lower and levels of high-density lipoprotein (HDL) cholesterol were statistically significantly higher in drug-treated subjects than in placebo-treated subjects, potentially representing additional anti-inflammatory activity of ADX-629.

#### 3.3 Trial Rationale

Chronic cough has been associated with autoimmune disease (Birring et al., 2003a). By covalently binding proteins and forming non-self-epitopes, RASP is associated with autoantibody formation (Thiele et al., 2015). In addition, chronic cough may be potentiated by the TRPV1 receptor (Long et al., 2019), which is modulated by RASP binding (Trevisani et al., 2007). Preliminary evidence also suggests that RASP is elevated in the sputum of patients with chronic cough (personal communication, [name]., National Jewish Medical Center) relative to control subjects. Thus, RASP inhibition could represent a novel approach for the treatment of chronic cough.

### 3.4 Benefit/Risk Assessment

The ADX-629-CC-001 clinical trial will evaluate the safety, tolerability, and efficacy of ADX-629 in subjects with refractory or unexplained chronic cough. The background and rationale detailed above suggests that subjects may benefit from treatment with ADX-629.

Safety of the clinical dosing regimen in this trial is supported by a Phase 1 clinical trial in healthy volunteers and a number of nonclinical toxicology and PK studies in which no serious safety concerns were noted at the projected therapeutic doses in man.

ADX-629 was well tolerated in healthy human volunteers at doses of up to 600 mg BID (the maximum dose tested) for 10 days. The AE profile of ADX-629 in the SAD/MAD studies was favorable compared to placebo: a total of 6 subjects (9.4%) who received ADX-629 had TEAEs, compared to 4 subjects (19.1%) who received placebo. There were no interruptions or discontinuations of trial drug administration with subjects receiving multiple doses. More information is provided in the current version of the Investigator's Brochure.

CONFIDENTIAL Page 23 of 68

Flexibility in the format of visits is built into this protocol to facilitate the health and safety practices necessary to protect everyone involved in the trial from transmission of COVID-19 or other infections. Throughout the protocol, the term 'visit' is used to indicate interaction between the trial subject and research staff. However, trial subjects are not required to attend the clinic but may be visited at home, or at another suitable location, by, e.g., a research nurse or other appropriate member of the research team, whenever the protocol assessments allow. Other arrangements are also permitted where these will not challenge the integrity of the data, e.g., couriers may be used for distribution and collection of cough monitoring equipment to the investigative site to minimize face-to-face contact. All research staff will employ routine personal protection, hand sanitization measures, and any other applicable local guideline requirements when in close contact with trial subjects.

CONFIDENTIAL Page 24 of 68

### 4. TRIAL OBJECTIVES AND ENDPOINTS

# 4.1 Objectives

## 4.1.1 Primary Objective

The primary objective of this trial is:

• To evaluate the safety and tolerability of ADX-629 300 mg administered orally BID for 2 weeks in adult subjects with refractory or unexplained chronic cough

# 4.1.2 Secondary Objectives

The secondary objectives of this trial are:

- To evaluate the efficacy of ADX-629 300 mg administered orally BID for 2 weeks in adult subjects with refractory or unexplained chronic cough
- To investigate the effect of ADX-629 300 mg administered orally BID for 2 weeks on the cough-related quality of life of adult subjects with refractory or unexplained chronic cough

## 4.2 Endpoints

# 4.2.1 Primary Endpoints

The primary endpoints of this trial are:

- Incidence and severity of TEAEs and serious adverse events (SAEs)
- Observed values and changes from baseline of:
  - Laboratory safety parameters
  - Vital signs
  - 12-lead electrocardiogram (ECG) parameters

## 4.2.2 Key Secondary Endpoint for Assessment of Efficacy

The key secondary efficacy endpoint for assessment of efficacy of this trial is:

• Change from baseline in awake cough frequency per hour after 2-week treatment

## 4.2.3 Secondary Endpoints

The secondary endpoints of this trial are:

- Change from baseline in 24-hour cough frequency per hour after 2-week treatment
- Change from baseline in cough severity using a visual analog scale (VAS)
- Change from baseline in LCQ scores
- Change from baseline in Cough-Specific Quality of Life Questionnaire (CQLQ) scores
- Global rating of change scores for cough severity and frequency
- Patient Global Impression of Change (PGIC) score
- Clinician Global Impression of Change (CGIC) score

CONFIDENTIAL Page 25 of 68

Should a subject discontinue trial treatment, they will be requested to participate in an early termination visit as soon as possible after the subject stops taking trial treatment. They should then have their end-of-trial visit approximately 14 days after their last dose of trial treatment; however, if their early termination visit is more than 1 week after their last dose, they will not be required to have a follow-up safety assessment.

The end-of-trial safety assessment will be conducted as a clinic visit for end-of-trial laboratory parameters, vital signs, or ECG parameters. The trial design is illustrated in Figure 1.

CONFIDENTIAL Page 26 of 68

Figure 1: Schematic of Trial Design

Abbreviation: BID=twice daily.

Subjects will attend the clinic or be visited by research staff, on consecutive days. The cough recorder will be fitted at screening, on Day 0, and Day 13 of each treatment period, to enable cough count data recording over a period of 24 hours.

## **5.2** Trial Visit Schedule

# 5.2.1 Summary of the Schedule of Assessments

A summary of the trial assessment schedule is provided in Table 1.

CONFIDENTIAL Page 27 of 68

Aldeyra Therapeutics, Inc.

Clinical Trial Protocol: ADX-629-CC-001

Version 2.0, 16 June 2022

**Table 1: Schedule of Assessments** 

CONFIDENTIAL Page 28 of 68

Aldeyra Therapeutics, Inc.

Clinical Trial Protocol: ADX-629-CC-001

Version 2.0, 16 June 2022

CONFIDENTIAL Page 29 of 68

Aldeyra Therapeutics, Inc.

Clinical Trial Protocol: ADX-629-CC-001

Version 2.0, 16 June 2022

CONFIDENTIAL Page 30 of 68

### 5.2.2 Trial Visits

Visits may be conducted either at the clinic or at another location such as the subject's home, provided the equipment is available to perform the required assessments.

# 5.2.2.1 Screening Period Procedures - Visit 1

Visit 1 may have a duration of more than 1 day to accommodate all screening assessments; the informed consent form (ICF) signature is the start of the screening period and will be used as the date of Visit 1. Subjects who are willing to participate will sign the ICF. Subjects will then be given a trial number before the screening evaluation procedures are performed. Each subject will be given detailed information about the trial, including timelines, description of each planned visit, possible side-effects, and potential benefits. The information given to each subject will be both oral and written.

- Obtain written informed consent after review of inclusion and exclusion criteria.
- Collect demographic information (date of birth, sex, ethnicity, and race).
- Medical history, including history of chronic cough, smoking history, and medication history.
- Collect vital signs (blood pressure, heart rate, respiratory rate, temperature, and oxygen saturation).
- Record concomitant medications.
- Conduct physical examination, including review of the major body systems, and record height and weight. Body mass index (BMI) will be calculated.
- Record standard 12-lead ECG.
- Record spirometry (forced expiratory volume in 1 second [FEV1] and forced vital capacity [FVC]).
- Review of chest radiograph or computed tomography (CT) scan of the thorax, done within 5 years before screening and after the onset of chronic cough. If a chest radiograph or CT have not done within the last 5 years, the subject is ineligible.
- Collect blood sample for routine laboratory testing (biochemistry and hematology). Testing to include follicle-stimulating hormone (FSH) in females thought to be menopausal and human chorionic gonadotropin (b-hCG) in women of childbearing potential, and Hepatitis B, C, and HIV serology in all subjects.
- Collect urine sample for urinalysis and urine/creatinine ratio.
- Perform urine drug screen.
- Perform alcohol breath test.
- Perform SARS-CoV-2 test (not required if the subject has had a negative SARS-CoV-2 test within 48 hours prior to date of informed consent signature). Results obtained by antigen testing or polymerase chain reaction testing are acceptable.
- Record cough severity VAS.
- Complete LCQ.
- Complete CQLQ.
- Record any pre-treatment AEs with onset after the subject has signed the ICF.

CONFIDENTIAL Page 31 of 68

• Subjects will be fitted with a cough recorder by 10:00 am, which must be worn for 24 hours of recording time. The cough recorder may be returned to the investigative site by courier after the 24-hour recording.

Subjects who fulfill the trial eligibility criteria will be given appointments for their participation in the trial.

If a subject visit falls outside the screening period window or repeat assessments are required, screening may be extended with approval from the Medical Monitor. If extended beyond 21 days, some of the screening procedures and assessments may need to be repeated.

Subjects who have screen failed may be re-screened once if their eligibility characteristics have changed. Subjects who are re-screened must be assigned a new subject number. The re-screening process for such subjects must be discussed with the Medical Monitor.

## 5.2.2.2 Randomization (Day 0)

The inclusion and exclusion criteria will be reviewed to confirm the subject's eligibility for the trial. Eligible subjects will be randomized to one of the two treatment sequences according to the randomization schedule.

### 5.2.2.3 Treatment Period Procedures - Visits 2 and 6

This visit may be conducted at the clinic or another location such as the subject's home, according to the preference of the subject.

The following assessments and procedures will be performed:

- Collect vital signs (blood pressure, heart rate, respiratory rate, temperature, and oxygen saturation).
- Record changes in concomitant medications.
- Record any AEs since the last visit.

Subjects should be fitted with a cough recorder by 10:00 am. The cough recorder must be worn for 24 hours between fitting and disconnection.

### 5.2.2.4 Treatment Period Procedures - Visits 3 and 7

The following assessments and procedures will be performed:

### Before Dosing:

- Review inclusion and exclusion criteria (Visit 3 only).
- Collect vital signs (blood pressure, heart rate, respiratory rate, temperature, and oxygen saturation).
- Record changes in concomitant medications.
- Symptomatic physical examination may be performed, if deemed necessary (e.g., to record any changes since screening or due to an AE). This may require an additional visit to the investigative site.

CONFIDENTIAL Page 32 of 68

- Record standard 12-lead ECG.
- Collect blood sample for routine laboratory testing (biochemistry and hematology).
- Collect urine sample for urinalysis and urine/creatinine ratio.
- Perform urine pregnancy test (women of childbearing potential).
- Perform urine drug screen.
- Perform SARS-CoV-2 test (Day 1 of Treatment Period 2 only).
- Record cough severity VAS.
- Complete LCQ.
- Complete CQLQ.
- Record any AEs since the last visit.
- The cough recorder will be disconnected 24 hours after fitting and retained by the investigative site.
- The first dose of trial treatment will be dispensed, and subjects will take the first dose (this must be after the completion of the cough monitoring).
- Visit 7 only: Unused trial medication and empty containers from Treatment Period 1 will be returned.

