## After Dosing:

• Collect vital signs (blood pressure, heart rate, respiratory rate, temperature, oxygen saturation) and record at 2 hours (±30 minutes) after dosing.

Subjects will be instructed to take the last dose of trial treatment in the evening at the usual time.

## 5.2.2.7 End-of-Trial visit - Visit 10

The following assessments and procedures will be performed at the clinic:

- Collect vital signs (blood pressure, heart rate, respiratory rate, temperature, and oxygen saturation).
- Record changes in concomitant medications.
- Conduct physical examination, including review of the major body systems.
- Record standard 12-lead ECG.
- Collect blood sample for routine laboratory testing (biochemistry and hematology).

CONFIDENTIAL Page 34 of 68

- Collect urine sample for urinalysis and urine/creatinine ratio.
- Record any AEs since the last visit.
- Unused trial medication and empty containers from Treatment Period 2 will be collected or returned.

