## 6.5 Removal of Subjects from Therapy or Assessment

Participation in the trial is strictly voluntary. A subject has the right to withdraw from the trial at any time and for any reason. If they choose to withdraw from the trial, the Investigator must be informed immediately. The Investigator has the right to terminate participation of any subject at any time if it is in the subject's best interest. The reason and circumstances for premature discontinuation will be documented in the subject's electronic case report form (eCRF).

A subject may be discontinued from treatment for any of the following reasons:

- Withdrawal of consent by the subject.
- Severe lack of compliance with trial treatment in Treatment Period 1 (i.e., <80% or >120% compliance).
- Increase from baseline in serum creatinine by  $\geq 0.3$  mg/dL or  $\geq 50\%$ .
- Major protocol deviation, e.g., requirement for a disallowed concomitant medication or non-drug therapies (see Table 3, Section 10.1.2).

CONFIDENTIAL Page 38 of 68

- Trial treatment must be discontinued in subjects who become pregnant in the trial. The pregnancy will be reported and followed up as per guidance in (see Section 8.3.2). However, the subject should still undergo relevant post-randomization procedures and visits if possible and safe to do so.
- Investigator's decision that it is not in the best interest of the subject to continue.
- Lost to follow-up: The subject stopped coming to the investigative site for visits, and trial personnel were unable to contact the subject.

Immediate safety concerns should be discussed with the Sponsor immediately upon occurrence or awareness to determine if the subject should continue or discontinue trial treatment.

If possible, an early termination visit should be conducted (i.e., procedures for the end of Treatment Period 1 Visit 4 or Treatment Period 2 Visit 8). The subject will be permanently discontinued from the trial treatment but will continue to be observed for AEs, if possible, until the scheduled end-of-trial visit (Visit 10).

If the subject withdraws consent for disclosure of future information, the Sponsor may retain and continue to use any data collected before such a withdrawal of consent.

If a subject withdraws from the trial, they may request destruction of any samples taken and not tested, and the Investigator must document this in the investigative site trial records.

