7.4 Selection of Doses and Timing of Dose for Each Subject

## 7.5 Packaging and Labeling

The Sponsor will be responsible for ensuring that ADX-629 and placebo tablets are manufactured in accordance with applicable current Good Manufacturing Practice regulations and requirements.

CONFIDENTIAL Page 42 of 68

ADX-629 tablets or placebo will be provided in treatment kits for each period between trial visits. Each of the product bottles is capped with a child-resistant closure liner with an induction seal.

The IP will be administered as 300 mg tablets, i.e., one tablet BID for 14 days. BID dosing means every  $12 (\pm 1)$  hours. Each container will hold sufficient tablets to cover the time until the next scheduled visit, plus overage in case the scheduled visit is delayed.

The IP will be labeled according to the requirements of local law and legislation.

Further details regarding packaging, labeling and accountability are provided in the pharmacy manual.

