#### 7.6 Storage, Handling, and Dispensing of Investigational Products

Investigational product will be shipped from the Sponsor's storage direct to investigative sites as soon as subject screening commences at the site. Each investigative site will maintain an inventory record of the kits received and dispensed.

Treatment kits will be dispensed to trial subjects as follows:

- Visit 3, Day 1 of Treatment Period 1: ADX-629 300 mg or placebo (one tablet) BID dosing for 14 days.
- Visit 7, Day 1 of Treatment Period 2: placebo or ADX-629 300 mg (one tablet) BID dosing for 14 days.

The IP will be provided to trial subjects only, i.e., eligible subjects who have provided written, informed consent and have been randomized.

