## 7.8 Treatment Compliance

The prescribed dosage, timing, and mode of administration of trial treatment should not be changed from the protocol schedule. Departures from the intended regimen will be reported as protocol noncompliance. Subjects must return empty containers and unused trial treatment as compliance will be assessed by tablet counts.

The Investigator or designee will assess the subject's compliance by performing a tablet count on return of unused trial treatment. Subjects who exhibit poor compliance, i.e., not 100% compliant without adequate explanation, should be counseled on the importance of good compliance with the dosing regimen. Severe lack of compliance is defined as <80% or >120% of the correct dosing and is a reason for discontinuation of the subject from the trial (Section 6.5).

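### Period 1 tablets are returned only at Visit 7, so the compliance count comes after the Period 2 baseline and cannot separate Period 1 use from washout use

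*Protocol*

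**What the plan says.** **Supply.** Protocol 7.6 dispenses the Period 1 kit once: "Visit 3, Day 1 of Treatment Period 1: ADX-629 300 mg or placebo (one tablet) BID dosing for 14 days". Section 7.5 adds "plus overage in case the scheduled visit is delayed", without giving a quantity.

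**End of Period 1.** On Day 14 (Visit 5, section 5.2.2.6) staff see the subject before and after the morning dose. The final dose is taken later at home: "Subjects will be instructed to take the last dose of trial treatment in the evening at the usual time". No return or count is listed at Visit 4 or Visit 5.

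**Period 2 baseline.** At Visit 6 (section 5.2.2.3), "Subjects should be fitted with a cough recorder by 10:00 am"; the recorder comes off at Visit 7. Under 8.1.1 this recording is the Period 2 baseline for awake cough frequency. No return is listed at Visit 6.

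**Return.** Section 5.2.2.4 has the line "Visit 7 only: Unused trial medication and empty containers from Treatment Period 1 will be returned". It sits under the *Before Dosing* heading, but below the bullet in which the first Period 2 dose is taken. For Period 2, section 5.2.2.7 (Visit 10) says "Unused trial medication and empty containers from Treatment Period 2 will be collected or returned".

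**Use of the count.** Section 7.8 assesses compliance by "performing a tablet count on return of unused trial treatment" and calls for counselling of poor compliers. Section 6.5 lists "Severe lack of compliance with trial treatment in Treatment Period 1" (under 80% or over 120%) as a reason for which treatment may be discontinued. Section 7.8 gives the same limits without naming a period, and as a reason for discontinuation from the trial.

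**The concern.** A two-period crossover relies on a drug-free washout and a clean second baseline. Subjects in the ADX-first sequence may hold active tablets throughout the washout, while those in the other sequence hold placebo. Any contamination of the Period 2 baseline by active drug would therefore fall on one sequence only, and would enter the model through the period-specific baseline.

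Timing is the second issue. The Period 1 criterion and the counselling step are useful if the count reflects Period 1 and is known before Period 2 starts. A count about 14 days after dosing ended mixes two intervals, and it arrives once the Period 2 baseline has been recorded. Subjects who skipped doses in Period 1 hold the most leftover tablets, so they have the most room for a misleading count.

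**Working it through.** The plan states no figure of its own on this point, so the check is tablet arithmetic followed by an estimate of consequence.

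**1. Limits.** Prescribed: 14 days × 2 = 28 tablets. 80% is 22.4 and 120% is 33.6. Hence 23 to 33 used tablets pass (23/28 = 82.1%; 33/28 = 117.9%), while 22 (78.6%) and 34 (121.4%) fall outside.

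**2. Under-use masked.** 22 tablets in Period 1 is 78.6%, below the limit. Six remain from the prescribed 28. If they are taken in washout, the Visit 7 count gives (22 + 6)/28 = 100%. No overage is needed.

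**3. Over-use in washout.** Suppose all 28 are taken in Period 1 and the whole overage in washout. The overage is not stated, so a range is assumed:

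| Overage (tablets) | Count at Visit 7 |
|---|---|
| 2 | 30/28 = 107.1% |
| 4 | 32/28 = 114.3% |
| 5 | 33/28 = 117.9% |
| 6 | 34/28 = 121.4% |
| 8 | 36/28 = 128.6% |

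Four tablets would cover the two-day margin in Protocol 7.1 (2 × 2 = 4). Up to five pass unflagged; six or more are flagged.

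**4. The SAP denominator.** SAP section 14 takes prescribed tablets as (last minus first administration) × 2.
- Day 1 morning to Day 14 evening is 13.5 days, so full adherence reads 28/27 = 103.7%. On 27, the masking pattern is the same with slightly different counts: 21/27 = 77.8% becomes 28/27 = 103.7% with 7 more in washout, and the largest unflagged excess is 4 (32/27 = 118.5%; 33/27 = 122.2%).
- Twice-daily dosing that simply runs on to 33 tablets spans 32 × 0.5 = 16 days and reads 33/32 = 103.1%, like a compliant course.
- If the last dose is correctly dated Day 27 evening, the duration is 26.5 days. Then 28/53 = 52.8% and 33/53 = 62.3%, both in the SAP's lowest band (70% or less).

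So the formula shows late intake only if the last-dose date is recorded correctly, and it does not show run-on.

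**5. Which intake could matter.** Protocol 3.2 gives mean half-lives of 3.49 to 6.83 h. Five half-lives are 17.5 to 34.2 h. A washout of 12 to 16 days is 42 half-lives (12 × 24/6.83) to 110 (16 × 24/3.49). On plasma levels, only tablets taken within about 1.5 days before the Visit 6 to 7 recording, or during it, would leave material drug. The run-on in step 4 ends about 2.5 days into washout. Even a 12-day washout then leaves 9.5 × 24/6.83 ≈ 33 half-lives. Duration of pharmacodynamic effect is not given.

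**6. Illustrative bias.** All inputs here are assumed: a true reduction of 35% (d = −ln 0.65 = 0.431); a fraction f = 5% to 20% of the ADX-first sequence with a fully treated Period 2 baseline; and a slope b = 0.5 to 0.9 of end-of-period on baseline log frequency. Bias ≈ f × b × d/2, which gives 0.0054 (f = 5%, b = 0.5) to 0.0388 (f = 20%, b = 0.9). The estimated reduction becomes 1 − exp(−(d + bias)) = 35.3% to 37.5%.

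**The case against.** The plan has real safeguards. Subjects are told when to take the last dose. SAP section 14 needs a date and time of last administration, so that date should be in the data, and one past Day 14 is itself evidence of run-on. The Visit 7 count still shows gross over-use. One tablet must stay with the subject after Visit 5, so collecting everything at the next dispensing visit is a defensible convenience. The schedule table is redacted in both documents and 7.5 defers accountability detail to the pharmacy manual, so a count at Visit 5 cannot be excluded.

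These points rule out three stronger readings that a reader might infer:
- *The washout is unverified.* Too strong: total use and a reported last-dose date are available. What is missing from the readable text is a dated check. It mentions no dosing diary or washout visit, and Protocol 8.2 rules out drug levels.
- *A non-compliant subject will already have taken a Period 2 dose.* Not established. Bullet order suggests it; the *Before Dosing* heading suggests the opposite.
- *Such a subject would have no Period 2 outcome.* Also too strong. The early withdrawal visit (5.2.2.8) collects the severity VAS, LCQ, CQLQ and global ratings. Its list has no cough recording.

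The Period 2 return at Visit 10 matters little, because no later period or baseline depends on it. None of this lets a Visit 7 count separate Period 1 tablets from washout tablets, or makes it available before the Period 2 baseline.

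**Conclusion.** The point holds in a limited form. On the readable visit text, Period 1 tablets stay with the subject through the washout and the Period 2 baseline recording. The resulting count measures total use without dating it. The Period 1 criterion is therefore read after that baseline and can be masked in either direction: 78.6% can read as 100%, and up to five washout tablets can pass at 117.9%. The second figure assumes at least five overage tablets, and both assume a denominator of 28. Whether the criterion is read before the first Period 2 dose is ambiguous.

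The likely effect on the efficacy estimate is small: in the illustration a 35% reduction becomes at most 37.5%, and only if intake occurred close to the recording. This is an inexpensive weakness in compliance checking and does not undermine the crossover. The conclusion would change if the redacted schedule table lists a count at Visit 5.

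**What to change.** - **Protocol 5.2.2.6, Visit 5:** after the morning dose, count the remaining tablets and collect all except the one for that evening. Base Period 1 compliance on this count plus the reported final dose, so that it is known before Visit 6.
- **Protocol 5.2.2.4, Visit 7:** move the return line above the first-dose line. Before dispensing the Period 2 kit, collect the Period 1 container and confirm the date of the last Period 1 dose.
- **Protocol 5.2.2.4, 6.5 and 7.8:** reconcile these on when the count is made and acted on, and on the period and the kind of discontinuation that the limits refer to. The limits and their consequence are left as they are.
- **Visit 9:** the same count is optional.

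The SAP numerator (dispensed minus returned) still works if tablets collected at Visit 5 count as returned. The cost is a wording change in the protocol and pharmacy manual and a few minutes at a visit already scheduled. The downside is that the final evening tablet is confirmed only by report and by the empty container.
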